## 4 STUDY DESIGN

This is a phase II, open-label trial to evaluate valganciclovir as a treatment to prevent development of SNHL in infants with asymptomatic congenital CMV infection. The trial will be conducted in two phases (screening of newborns to identify eligible subjects, and treatment of those newborns who have confirmed CMV infection at birth but without outward manifestations of congenital CMV infection).

Following consent for *screening*, newborns with no outward manifestations of congenital CMV infection who are delivered at one of 9 participating academic medical centers will be screened for CMV infection during their birth hospital stay. A buccal saliva swab will be obtained by swabbing the inside of the newborn's mouth for detection of CMV by PCR. The collected swabs will be transported within 4 days of collection to the Central Laboratory at the University of Alabama at Birmingham for testing. Babies screening positive for congenital CMV infection will have a second saliva sample and a urine sample collected for confirmatory PCR testing. Study drug will not be started until the confirmatory PCR testing is completed; the likelihood of a false-positive screening test is < 0.03%, but performing a confirmatory test ensures that only those babies truly infected with CMV will be exposed to valganciclovir. Approximately 48,250 newborn infants will be screened to detect approximately 241 neonates with asymptomatic congenital CMV infection; these 241 newborns then will have audiology examinations to determine baseline hearing, with approximately 229 having normal hearing in both ears. Those 229 newborns with confirmed CMV infection but without baseline SNHL and who meet all inclusion/exclusion criteria will be offered enrollment into the treatment phase.

Through this screening process, approximately 12 neonates congenitally infected with CMV who have SNHL at birth also will be identified. Newborn patients with SNHL and who are being treated clinically with valganciclovir will be offered enrollment into an *observational* substudy as detailed below.

After obtaining *treatment* informed consent, enrolled subjects will be treated for four months with oral valganciclovir (16 mg/kg/dose, administered two times per day). **Study Day 1** is the day that the first dose of study medication is administered. Audiologic assessments will be made during the Screening Period and Study Months 4 (end of treatment), 6, 12, and 18. A single, independent study audiologist will assess the audiology test battery for each subject and assign each ear the classifications of normal hearing, mild hearing loss, moderate hearing loss, severe hearing loss, or profound hearing loss based upon their hearing thresholds (in decibels). If a study subject proceeds to cochlear implantation during the course of the study, he/she will not require additional study-related hearing assessments following the implantation procedure but will continue with all other study-related assessments.

Treated infants will be followed for safety throughout the first 6 months of the study (including for 2 months post-treatment). Hematology safety laboratory assessments will be obtained weekly for the first six weeks of study drug administration, then every other week for the next six weeks of study drug administration, and then at months 4 and 5. Chemistry safety laboratory

---

assessments will be obtained every other week for the first 12 weeks (3 months) of treatment, and then at months 4, 5, and 6. Adverse events will be assessed at each study visit during treatment, and at month 5.

Whole blood viral load and plasma viral load will be obtained at each study visit during the course of study drug administration, and then at Study Months 5 and 6. Specimens from subjects with increasing viral loads despite antiviral therapy may be evaluated for ganciclovir resistance by molecular methodologies (e.g., deep sequencing, Sanger sequencing, PCR). Urine and saliva will be obtained at Baseline and Study Months 4, 5, and 6 in order to obtain viral isolates to assist in detection of antiviral resistance.

#### **4.1 Substudies (if applicable)**

Infants with confirmed CMV but who have documented SHNL at baseline and who are being treated clinically with valganciclovir (expected to be about 12 patients) will be offered enrollment into an observational substudy. No additional audiologic or safety testing will be done as part of the study. However, available clinical audiologic and safety data will be redacted without alteration from the clinical medical record. Enrolled subjects will be followed for CMV viral load as part of the study. Viral loads would not be routinely followed as part of clinical management (and thus will be study procedures), whereas the valganciclovir treatment and associated safety labs as well as the serial hearing testing are part of clinical care for these patients. Blood for CMV viral load will only be obtained at a given study visit if other blood is being obtained by venipuncture for clinical purposes. Inclusion of these substudy subjects will enhance the understanding of antiviral effects on audiologic outcomes from congenital CMV infection, bridging the gap between the completely asymptomatic population in the main study and the symptomatic populations assessed in prior CASG trials.

---

## 5 STUDY ENROLLMENT AND WITHDRAWAL

### 5.1 Subject Inclusion Criteria

- Parent(s)/legal guardian(s) have signed informed consent documents\*
- Confirmation of CMV by urine PCR testing
- Infant  $\leq 30$  days of age at initiation of study drug
- Weight at study enrollment  $\geq 1775$  grams
- Gestational age  $\geq 32$  weeks at birth

\* There is a *screening* informed consent for screening phase of study participation, and a *treatment* informed consent for treatment phase of study participation.

### 5.2 Subject Exclusion Criteria

- Symptomatic congenital CMV disease\*
- Sensorineural hearing deficits as detected by formal brainstem evoked response (not a screening ABR) of known etiology other than CMV
- Prior or current receipt of ganciclovir, valganciclovir, foscarnet, cidofovir, brincidofovir, maribavir, or letermovir
- Maternal receipt of CMV hyperimmune globulin during pregnancy
- Breastfeeding from mother who is receiving ganciclovir, valganciclovir, foscarnet, cidofovir, brincidofovir, maribavir, or letermovir
- Gastrointestinal abnormality which might preclude absorption of an oral medication (e.g., a history of necrotizing enterocolitis)
- Infants known to be born to women who are HIV positive (HIV testing is not required for study entry)
- Current receipt of other investigational drugs

\* Symptomatic disease is defined as one or more of the following: 1) thrombocytopenia, if known; 2) petechiae; 3) hepatomegaly; 4) splenomegaly; 5) intrauterine growth restriction; 6) hepatitis (elevated transaminases and/or direct bilirubin), if known; 7) central nervous system involvement of the CMV disease (such as microcephaly; radiographic abnormalities indicative of CMV CNS disease, if known; abnormal CSF indices for age, if known; chorioretinitis, if known; and/or positive CMV PCR from CSF, if known).

### 5.3 Treatment Assignment Procedures

#### 5.3.1 Randomization Procedures

This is a single-arm study; subjects will not be randomized to treatment.

#### 5.3.2 Masking Procedures

This is a single-arm open-label study. No masking procedures will be done.

---

### 5.3.3 Reasons for Withdrawal

#### 5.3.3.1 Reasons for Withdrawal Prior to Initiation of Study Drug

The criteria for discontinuation of study participation following confirmation of congenital CMV infection in the *screening* process but prior to initiation of study medication in the *treatment* portion of the study:

- Study subject (parent/legal guardian) wishes to withdraw
- The study is terminated
- Any other reason which, in the opinion of the investigator, precludes the study subject's participation in the study. Note: The site principal investigator must call the study Principal Investigator (or designee) prior to discontinuing a study subject for this reason.

#### 5.3.3.2 Reasons for Withdrawal During Treatment

The criteria for discontinuations during the time that study medication is being provided include:

- Discontinuation of Study Product
  - Development of a related serious adverse event warranting withdrawal of therapy
  - Deterioration in general condition for which alternative treatment is indicated and which, in the opinion of the investigator, warrants withdrawal of therapy
  - Development of a medical disease or condition, or any new clinical findings for which continued participation, in the opinion of the site principal investigator or appropriate sub-investigator, would compromise the safety of the subject, would interfere with the subject's successful completion of this study, or would interfere with the evaluation of responses.
- Subject Withdrawal
  - Study subject (parent/legal guardian) wishes to withdraw
  - Non-compliance with study procedures or medication schedule that in the opinion of the investigator warrants withdrawal
  - The study is terminated
  - Any other reason which, in the opinion of the investigator, precludes the study subject's participation in the study. The site principal investigator must call the study Principal Investigator (or designee) prior to discontinuing a study subject for this reason.

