### **5.3.4 Handling of Withdrawals**

Study subjects may withdraw voluntarily from participation in the study at any time. Up to 20% over-enrollment is allowed to replace subjects who drop-out or who have inadequate audiology assessments. Study subjects also may withdraw voluntarily from receiving the study intervention for any reason. If a study subject withdraws from the study or discontinues study intervention at any time prior to completion of the study, the reason for this decision will be recorded on the appropriate electronic case report form (eCRF). SAEs and AEs will be followed according to guidelines in Section 9. The study subject should be asked to complete follow-up visits.

Should a study subject's therapy be discontinued prematurely, all clinical and laboratory evaluations scheduled during the next study visit will be completed on the day the study subject is discontinued. All enrolled study subjects will continue to be followed as long as possible.

Since the primary endpoint requires comparison of baseline and 6 month audiology assessments, dropouts and subjects with audiology assessments that are inadequate for study comparison (Section 11.2) will be replaced. Characteristics of the dropouts and those with missing outcomes will be compared to determine if there is a difference between the two treatment groups. If differences are observed, this will be included in the primary outcome reporting as a limitation.

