## 7.5 Early Termination Visit

Study subjects may withdraw voluntarily from participation in the study at any time. Study subjects may also withdraw voluntarily from receiving the study intervention for any reason. If a study subject withdraws or is discontinued from the study at any time prior to completion of the study, the reason for this decision will be recorded on the CRFs. The remaining follow-up evaluations will be conducted if patient consent is obtained. SAEs and AEs will be followed according to guidelines in Section 9. The study subject should be asked to complete follow-up visits.

Should a study subject's therapy be discontinued prematurely, all clinical and laboratory evaluations scheduled during the next study visit will be completed on the day the study subject is discontinued. All key endpoints will be evaluated and all randomized study subjects will continue to be followed as long as possible and included in the final analysis.

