## **9.5 Halting Rules**

### **9.5.1 Discontinuation of Study Participation for Individual Subject**

Subjects with neutropenia, thrombocytopenia, or hepatotoxicity while on study medication will be discontinued from study treatment if the criteria outlined in Section 6.3 (Modification or

---

Termination of Study Intervention/Investigational Product for a Participant) or in Section 5.3.3 (Reasons for Withdrawal) are met. Since the primary endpoint requires comparison of baseline and 6 month audiology assessments, dropouts and subjects with audiology assessments that are inadequate for study comparison will be replaced in order to reach the target of sample size.

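### Sections 5.3.3.2, 5.3.4, 7.5, 9.5.1 and 11.4.1.2 disagree on whether an infant withdrawn for missed medication is followed, replaced and counted in the Month 6 hearing result

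*Combined protocol and SAP*

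**What the plan says.** Section 5.3.3.2 has two lists for the treatment period, one for stopping the study product and one for subject withdrawal. The second contains "Non-compliance with study procedures or medication schedule that in the opinion of the investigator warrants withdrawal". It sets no threshold for missed doses and, unlike the any-other-reason item in the same list, asks for no prior call to the study's principal investigator. Section 5.3.2 confirms the setting: "This is a single-arm open-label study. No masking procedures will be done".

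Section 5.3.4 says "All enrolled study subjects will continue to be followed as long as possible" and, of those who withdraw or stop the drug, "The study subject should be asked to complete follow-up visits". It also says "dropouts and subjects with audiology assessments that are inadequate for study comparison (Section 11.2) will be replaced", within a 20% over-enrollment limit.

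Section 7.5 covers a subject who withdraws or is discontinued from the study: "The remaining follow-up evaluations will be conducted if patient consent is obtained". It adds that "all randomized study subjects will continue to be followed as long as possible and included in the final analysis".

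Section 9.5.1 has a heading about discontinuing study participation. Its text says that infants with the named toxicities stop study treatment if the criteria in 6.3 or 5.3.3 are met, and then that "dropouts and subjects with audiology assessments that are inadequate for study comparison will be replaced".

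Section 11.4.1 defines one efficacy population, per protocol, made up of children who complete the four months of drug. Intention to treat is defined for safety only. Section 11.4.5 imputes no missing hearing data.

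**The concern.** The primary result is a proportion with a small numerator, compared with a fixed historical figure. Who is in the denominator matters as much as how hearing is measured.

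Read together, these sections give a site no single answer for an infant whose family misses many doses. The infant may leave the study and be replaced, stay and be counted, or be followed and then fall outside the efficacy population. The first and third outcomes remove infants with poor drug exposure from the primary estimate. The decision to withdraw rests with an unmasked investigator.

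If poor adherence goes with a higher risk of hearing loss, because the drug works or because adherence tracks prognosis, the Month 6 rate would be too low and the error would favour the benefit conclusion.

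**Working it through.** **1. One infant, five sections.** Take an infant withdrawn for missed doses whose parents still agree to the Month 6 hearing test.

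| Section | Followed? | Replaced? | Counted? |
|---|---|---|---|
| 5.3.3.2 | participation ends | not stated | not stated |
| 5.3.4 | yes, as far as feasible | yes, if a dropout (undefined) | not stated |
| 7.5 | yes, with consent | not stated | yes |
| 9.5.1 | 5.3.3 reasons stop treatment only | yes, if a dropout (undefined) | not stated |
| 11.4.1.2 | not relevant | not relevant | no, four months of drug not completed |

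Section 11.2 adds another reading. Its chain is 229 − 11 = 218, 218 − 22 = 196, 196 − 20 = 176. The losses are refusal, no 6-month hearing test, and inadequate hearing data. No step removes infants who did not complete the drug, so evaluable in 11.2 depends on audiology, whereas 11.4.1.2 depends on drug completion.

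**2. The plan's bounds.** The one-sided 95% Clopper-Pearson upper bound for x cases in n is the 0.95 quantile of Beta(x + 1, n − x). With n = 176:

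- x = 0: 1.69% (plan: 1.69%)
- x = 1: 2.67% (plan: 2.67%)
- x = 2: 3.53% (Table 3: 3.50%, a small discrepancy that does not alter the conclusion)

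Against the 3.18% benchmark, zero or one case meets the criterion and two cases fail it.

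**3. Chance of meeting the criterion when the true rate is 3.18%.**
P(X ≤ 1) = 0.9682^176 + 176 × 0.0318 × 0.9682^175 = 0.0034 + 0.0196 = 2.3%.

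**4. What replacement could do.** The inputs below are assumptions, because the documents give none.

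- *No drug effect, adherence unrelated to risk.* Replacements carry the same risk as those removed. The chance stays at 2.3%.
- *No drug effect, but a fraction g of would-be cases is removed and replaced.* The rate becomes p(1 − g)/(1 − pg) with p = 0.0318. For g = 10%, 20% and 30% it is 2.87%, 2.56% and 2.25%, and the chance of meeting the criterion is 3.7%, 5.9% and 9.2%.
- *Drug works.* Suppose 10% of infants are poorly treated and carry 3.18%, and the rest carry 1%. Counting all infants, the rate is 0.10 × 3.18% + 0.90 × 1% = 1.22% and the chance is 36.7%. With the poorly treated replaced, the rate is 1% and the chance is 47.4%. If 5% or 15% are poorly treated, the chance with all counted is 41.8% or 32.1%.

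**The case against.** The strongest reply is that Section 7.5 already covers most of this. It applies to infants discontinued from the study and provides for their remaining evaluations if consent is given, so withdrawal need not lose the Month 6 test. Sections 5.3.4 and 9.5.1 justify replacement by the need for baseline and 6-month audiology, so the natural meaning of dropout is an infant without it. That stands as the likely intention. It is not stated, and 11.4.1.2 would exclude such an infant even if the test were done.

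Section 5.3.4 also requires reasons to be recorded, and dropouts and those with missing outcomes to be compared, with differences reported as a limitation. But that comparison is between two treatment groups, which a single-arm trial does not have, and it cannot recover a test that was never done.

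Three stronger readings are tempting, and the documents do not support them.

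- *The investigator withdraws non-compliant infants knowing their Month 4 hearing.* The criterion applies while drug is being given. The Month 4 test falls at the end of treatment, with a window opening 10 days before, so overlap is limited to about the last 10 days of dosing. One independent audiologist classifies hearing. Selection through this item would be mainly by adherence. The any-other-reason item in 5.3.3.3 can operate after Month 4, but it requires a call to the study's principal investigator.
- *The chance that a withdrawn group contains a case measures the bias.* For all 22 infants expected to lack the Month 6 test, 1 − 0.9682^22 = 51%. This is only the chance that any 22 infants at that risk include a case. If replacements carry the same risk, the expected rate does not change. No section attributes all 22 losses to investigator withdrawal.
- *Section 5.3.4 promises that every infant is analysed.* It promises follow-up only. Section 7.5 alone mentions the final analysis, and it speaks of randomized subjects in a trial without randomization.

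**Conclusion.** The concern holds as a conflict between sections on who is followed, replaced and counted. It leaves a route by which infants with poor drug exposure can leave the primary denominator and be replaced.

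Any bias depends on adherence being related to the risk of hearing loss. If it is, the direction is probably downward, toward the benefit conclusion. Neither the number of such withdrawals nor the strength of that relation is in the documents, so the size cannot be computed. The scenarios above show only what assumed values would imply.

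The point deserves correction because the criterion turns on a single case, 2.67% against 3.53%. One removed case reverses the conclusion only when exactly two would otherwise be counted. At a true rate of 3.18% that has probability C(176, 2) × 0.0318² × 0.9682^174 = 5.6%. Section 11.4.1.2 is the more direct conflict with 7.5, and correcting 5.3.3.2 alone would leave it in place.

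**What to change.** Reconcile Sections 5.3.3.2, 5.3.4, 7.5, 9.5.1 and 11.4.1.2, leaving every criterion for stopping the drug as it is, so that:

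- (a) only withdrawal of parental consent or loss of contact ends hearing follow-up;
- (b) an infant withdrawn for non-compliance, or at the investigator's discretion, still has the Month 6 hearing test;
- (c) dropout, for replacement, means an infant without adequate baseline and Month 6 audiology;
- (d) every treated infant with adequate audiology counts in the primary analysis, and the four-month completers form a supportive analysis.

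The cost is protocol wording and a few extra follow-up contacts with less cooperative families. The visits and hearing tests are already scheduled, and the sample size of 176 does not change.

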#### 5.3.3.3 Reasons for Withdrawal After Completion of Treatment

Criteria for discontinuing study subjects from the study after study medication is complete are:

- Study subject (parent/legal guardian) wishes to withdraw
- Any other reason, which in the opinion of the investigator, should preclude the study subject's continued participation in the study. The site principal investigator must call the study Principal Investigator (or designee) prior to discontinuing a study subject for this reason.
- Any subject that is terminated due to loss to follow-up will be considered as withdrawn

---

### **5.3.4 Handling of Withdrawals**

Study subjects may withdraw voluntarily from participation in the study at any time. Up to 20% over-enrollment is allowed to replace subjects who drop-out or who have inadequate audiology assessments. Study subjects also may withdraw voluntarily from receiving the study intervention for any reason. If a study subject withdraws from the study or discontinues study intervention at any time prior to completion of the study, the reason for this decision will be recorded on the appropriate electronic case report form (eCRF). SAEs and AEs will be followed according to guidelines in Section 9. The study subject should be asked to complete follow-up visits.

Should a study subject's therapy be discontinued prematurely, all clinical and laboratory evaluations scheduled during the next study visit will be completed on the day the study subject is discontinued. All enrolled study subjects will continue to be followed as long as possible.

Since the primary endpoint requires comparison of baseline and 6 month audiology assessments, dropouts and subjects with audiology assessments that are inadequate for study comparison (Section 11.2) will be replaced. Characteristics of the dropouts and those with missing outcomes will be compared to determine if there is a difference between the two treatment groups. If differences are observed, this will be included in the primary outcome reporting as a limitation.

### **5.3.5 Termination of Study**

The ethics committees, FDA, UAB Central Unit, or DMID have the right to terminate this study at any time. Reasons for terminating the study may include, but are not limited to, the following:

- The incidence or severity of adverse events in this or other studies indicates a potential health hazard to study subjects
- Study subject enrollment is unsatisfactory
- Data recording is inaccurate or incomplete
- The Investigator has not been adhering to the protocol or applicable regulatory guidelines in conducting the study

---

